### **10.3.2. Protocol Deviations and Changes to Planned Analyses**

Permission from the sponsor in writing will be obtained should any changes be required to the clinical study protocol. Should the safety of the subjects necessitate immediate action, which represents a deviation from the clinical study protocol, the sponsor will be informed as soon as possible.

Protocol deviations will be tracked by the study team throughout the conduct of the study in accordance with the Protocol Deviation Management Plan .

Protocol deviations and changes to planned analyses will be described in the clinical study report.

### 10.3.3. PK Parameters

Calculation of the PK parameters will be made with Phoenix WinNonlin 6.3 (Certara, L.P., [name]). The PK parameters will be calculated for each subject and treatment using non compartmental analysis and using the actual sampling time intervals (relative to IMP administration).

#### 10.3.3.1. Primary Pharmacokinetic Parameters for ciprofloxacin

- Maximum observed plasma concentration ( $C_{\max}$ )
- Area under the plasma concentration versus time curve, from time zero to  $t$ , where  $t$  is the time of the last quantifiable concentration ( $AUC_{(0-t)}$ ).

#### 10.3.3.2. Secondary Pharmacokinetic Parameters for ciprofloxacin

- Time to maximum observed plasma concentration ( $t_{\max}$ )
- Area under the plasma concentration versus time curve, with extrapolation to infinity ( $AUC_{(0-\infty)}$ )
- Apparent terminal elimination half-life ( $t_{1/2}$ )
- Percent area under the curve extrapolated (% $AUC_{\text{ex}}$ ).

### 10.3.4. Analysis of Bioequivalence

**Table 7 Statistical Analysis Methods to be used for Endpoints**

Endpoint	Statistical Analysis Methods
Primary	
Following log-transformation of derived pharmacokinetic parameters <math>C_{\max}</math> and <math>AUC_{(0-t)}</math> of ciprofloxacin will be analysed by using analysis of variance with sequence, subject (sequence), treatment and period effects. Point estimates for the adjusted means on the loge scale, the mean difference between treatments and associated 90% CIs for the difference Treatment A - Treatment B will be constructed using the residual variance.
 
These point estimates and confidence intervals will then be exponentially back-transformed to obtain adjusted (least square) geometric means for each treatment and point estimates and associated 90% confidence intervals for the ratio, Treatment A/Treatment B.
 
Distributional assumptions underlying the statistical analyses will be assessed by visual inspection of residual plots. Normality will be examined by normal probability plots, while homogeneity of variance will be assessed by plotting the residuals against the predicted values for the model. If the assumptions are

Endpoint	Statistical Analysis Methods
	seriously violated then alternative statistical methods will be considered.
Secondary	AUC (0-∞) of ciprofloxacin will be analysed as per primary analysis; t max of ciprofloxacin will be analysed using a nonparametric test to compute point estimate of the median and associated 90% confidence intervals for the median differences, Treatment A –Treatment B %AUCex will not be statistically analysed. A summary will be created. For t½ the n, median, minimum, and maximum values will be presented

### 10.3.5. Safety Analyses

All safety analyses will be performed on the Safety Population.

Safety variables will include vital signs and clinical chemistry results. Adverse events and concomitant medication will also be listed and summarized by treatment.

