## 4. OBJECTIVES AND ENDPOINTS

**Table 3 Study Objectives and Endpoints**

Objectives	Endpoints
Primary  To determine if 500 mg Ciprofloxacin (GR37547) tablets are bioequivalent to reference 500 mg Ciprofloxacin tablets in healthy adult participants under fasting conditions.	Plasma PK parameters: $AUC_{(0-t)}$ and $C_{max}$ , for ciprofloxacin in relevant treatments.
Secondary  To assess secondary PK parameters of 500 mg ciprofloxacin tablets (GR37547) relative to reference 500 mg ciprofloxacin in healthy adult participants under fasting conditions .  To compare the safety and tolerability of a single dose of a 500 mg ciprofloxacin tablet (GR37547) with reference 500 mg ciprofloxacin tablet, in healthy adult participants under fasting conditions.	
 
Plasma PK parameters: <math>AUC_{(0-\infty)}</math>, <math>t_{max}</math>, <math>\%AUC_{ex}</math> and <math>t_{1/2}</math> for ciprofloxacin in relevant treatments.
 
Adverse events (AE), clinical laboratory values (Haematology and Biochemistry), ECGs and vital signs
 

$AUC_{(0-\infty)}$ = Area under the concentration-time curve from time zero (pre-dose) extrapolated to infinite time; $\%AUC_{ex}$ = Percentage of $AUC(0-\infty)$ obtained by extrapolation; $AUC_{(0-t)}$ = Area under the plasma concentration versus time curve from time zero to $t$ , where $t$ is the time of the last quantifiable concentration; $t_{1/2}$ = Terminal phase half-life $C_{max}$ = Maximum observed concentration; $T_{max}$ = Time of occurrence of $C_{max}$ .	

[figure not shown]

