### **Medical Conditions**

1. History or presence of cardiovascular, respiratory, hepatic, renal, gastrointestinal, endocrine, haematological, neuromuscular, psychiatric, auto-immune or neurological disorders .
2. History of convulsions.
3. Any other condition that is capable of significantly altering the absorption, metabolism, or elimination of drugs; constituting a risk when taking the study treatment; or interfering with the interpretation of data.
4. History of any malignancies or chemotherapy/radiation within the past 5 years excluding treated squamous carcinoma of the skin and adequately excised basal cell carcinoma
5. History of kidney, heart or lung transplants.
6. History or presence of rheumatoid arthritis.
7. Presence of hypokalaemia where the serum potassium is < lower limit of normal (LLN).
8. Presence of hypomagnesaemia where the serum magnesium is < LLN.
9. Fasting blood glucose  $\geq 7$  mmol/L.
10. Serum glucose-6-phosphate dehydrogenase < LLN.
11. Abnormal renal function, as determined by creatinine clearance and considered as clinically significant by the investigator will be excluded.
12. Alanine transaminase (ALT)  $> 1.5 \times$  upper limit of normal (ULN)

13. Bilirubin  $>1.5 \times \text{ULN}$  (isolated bilirubin  $>1.5 \times \text{ULN}$  is acceptable if bilirubin is fractionated and direct bilirubin  $<35\%$ ).
14. Current or chronic history of liver disease, or known hepatic or biliary abnormalities (with the exception of Gilbert's syndrome or asymptomatic gallstones)
15. Excessive alkalinity of the urine ( $\text{pH} \geq 9$ ), as determined on Day -1.
16. Abnormal blood pressure (BP) as determined by the investigator.
17. QT interval corrected for heart rate according to Bazett's formula ( $\text{QTcB} > 450$  milliseconds (msec)). Participants with a known risk of QT prolongation will be excluded.

NOTES:

- For purposes of data analysis, only  $\text{QTcB}$ , will be used.

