### 10.3.6. Other Analyses

No other analyses are planned.

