## **Presentation of Baseline Characteristics and Safety Data**

Baseline characteristics and safety data will be presented as mentioned below. Data captured but not presented as listed or summarized data will be available in the CRFs or the source data capture system.

Demographic and anthropometric data will be listed for all participants in the safety population. Demographic characteristics will be tabulated by treatment (n, mean, median, standard deviation, minimum and maximum for age and BMI; and frequency counts and percentages for race, age groups and sex).

Adverse events (AEs) will be coded using the Medical Dictionary for Regulatory Activities (MedDRA), and listed and summarized by treatment for all participants in the safety population.

Vital signs data will be listed and summarized for all participants in the safety population.

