### **Tables**

Demographic characteristics

Statistical analyses of ciprofloxacin PK parameters (ANOVA)

Non Parametric Analysis of ciprofloxacin PK parameter

Plasma ciprofloxacin concentration (unit)

Plasma ciprofloxacin PK parameter (unit)

Adverse events summary by treatment

Concomitant Medication summary by treatment

Summary Statistics of Vital Signs Values

Summary Statistics of Chemistry Values.

Summary Statistics of Haematology Values.

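### ECGs are a named secondary safety endpoint for comparing the two products, but the only planned ECG output is a listing; no by-treatment summary of the measured values is specified.

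*Combined protocol and SAP*

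**What the plan says.** Table 3 (section 4), repeated in the synopsis, states the secondary safety objective as "To compare the safety and tolerability of a single dose of a 500 mg ciprofloxacin tablet (GR37547) with reference 500 mg ciprofloxacin tablet". Its endpoints are "Adverse events (AE), clinical laboratory values (Haematology and Biochemistry), ECGs and vital signs".

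On analysis, section 10.3.5 states "Safety variables will include vital signs and clinical chemistry results" and "Adverse events and concomitant medication will also be listed and summarized by treatment". Section 10.3.6 adds "No other analyses are planned".

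Appendix 6 (section 12.6) sets out the outputs. Its text on safety data covers adverse events and vital signs: "Vital signs data will be listed and summarized for all participants in the safety population". Its table list includes "Summary Statistics of Vital Signs Values" and the equivalent for chemistry and haematology. There is no ECG table and no ECG figure. ECG is found only in the list of listings.

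Two places look ahead to an analysis of QT data. The note to exclusion criterion 17 in section 6.2 begins "For purposes of data analysis, only" and goes on to name QTcB. Section 8.1.2 requires one correction formula per participant for all QTc data gathered for analysis.

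**The concern.** An endpoint placed under an objective to compare two products should have a planned output that sets the products side by side. For ECG there is none. A team that follows the plan as written will collect the ECGs, list them, and report no QTcB or heart-rate result by product.

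The protocol treats the variable as important. Table 2 names QT prolongation as a risk and gives post-dose ECGs in each period as part of the mitigation. Section 8.1.2 has QTc withdrawal criteria. Section 9.4.3 times the Day 1 ECG to coincide with the expected peak concentration. What is at stake is one part of a secondary objective: shifts too small to be called clinically significant would be visible only to someone who tabulates the listing.

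**Working it through.** The plan gives no figure for ECG, so the main check sets endpoints against outputs.

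**Step 1. Match each safety endpoint in Table 3 to what is planned.**

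| Endpoint group | Named in 10.3.5 | Appendix 6 table | Appendix 6 listing |
|---|---|---|---|
| Adverse events | yes, by treatment | yes | yes |
| Biochemistry | yes | yes | yes |
| Haematology | no | yes | yes |
| Vital signs | yes | yes | yes |
| ECGs | no | **no** | yes |

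Haematology and biochemistry form one group in Table 3, so one of four groups has no summary. The haematology row shows that the section 10.3.5 sentence is not enough to establish the gap: a variable can be missing there and still have a table. The gap follows from section 10.3.5, the Appendix 6 text and the table list taken together.

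Urinalysis is also only listed, but Table 3 does not name it as an endpoint. Concomitant medication, which is not an endpoint either, gets a summary by treatment.

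**Step 2. Check that the data would support a comparison.** The Schedule of Activities places ECGs at screening, at 2 hours post dose on Day 1 of each period, and at discharge at the end of Period 2 only.
- The 2-hour ECG exists for both products: up to 26 × 2 = 52 recordings, or 22 × 2 = 44 with the minimum 22 completers.
- The discharge ECG exists for one product per participant and cannot support a within-participant comparison.
- Screening is the only ECG scheduled before dosing, and neither period has its own pre-dose ECG. Both periods therefore share one baseline S, and in a paired difference it cancels: (A − S) − (B − S) = A − B. Change from screening is useful for description and for counting large changes, but adds nothing to a paired contrast.

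**Step 3. Precision of an optional paired difference.** The documents give no within-participant SD for a single QTcB reading. I assume 10 to 15 msec. SE = SD × √2 / √n; the half-width of the 95% CI is t × SE.
- n = 26, t ≈ 2.06: SE = 10 × 1.414 / 5.099 = 2.8 msec and 15 × 1.414 / 5.099 = 4.2 msec. Half-width 5.7 to 8.6 msec.
- n = 22, t ≈ 2.09: SE = 3.0 to 4.5 msec. Half-width about 6.3 to 9.4 msec.

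**Step 4. Effect on the design.** The sample size in section 10.1 reproduces: with a CV of 18%, a true ratio of 0.95 and 0.05 per one-sided test, power is 0.899 at 20 participants and 0.924 at 22, so 22 is the smallest even number reaching 90%. It rests on Cmax and AUC(0-t) alone. An ECG table changes no sample size, power or alpha.

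**The case against.** Several counter-arguments have force.

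- **Section 10.3.5 does not restrict anything.** A reader might infer that it limits safety variables to vital signs and chemistry. Its wording is inclusive, and sections 10 and 10.3 refer to Appendix 6 for the outputs. This stands; the case has to be made from Appendix 6 as well.
- **ECG information is not lost.** A reader might infer that the ECG part of the objective cannot be answered at all. That is too strong. Appendix 4 makes ECG abnormalities judged clinically significant adverse events, and these are summarised by treatment. QTc withdrawals would show in the disposition listing. With about 26 participants, individual values can be read from the ECG listing. This also stands, and confines the gap to a planned summary of measured values.
- **A confidence interval for ECG alone exceeds the plan's standard.** No other safety variable gets a paired difference with an interval. This stands; the interval should be optional.
- **The comparison is not especially clean.** ECGs are single recordings with a ±30 minute window and no period-specific baseline. True, but these limits affect precision and baseline definition. They are not reasons to report no summary.
- **The QTcB note sits under an exclusion criterion and promises no table.** Taken alone it is weak support. Section 8.1.2 repeats the idea that QTc data are collected for analysis, so the two together show that an analysis was expected, without specifying one.

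None of these supplies a by-treatment summary of the ECG endpoint.

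**Conclusion.** The mismatch is real and minor. One of four named safety endpoint groups, under an objective worded as a comparison, has a listing and no planned summary. The finding rests on the documents alone. Only the illustrative precision of about 6 to 9 msec depends on the assumed SD of 10 to 15 msec, and no decision rule in the protocol uses that interval.

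The documents do not support reading this as a failure of safety monitoring or as a weakness in the bioequivalence assessment. ECGs are recorded, clinically significant findings are reported as adverse events, and bioequivalence is judged on Cmax and AUC(0-t) only. This is a worthwhile improvement to the plan, not a condition for running the study.

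**What to change.** Name ECG in section 10.3.5 and add one descriptive table by treatment to Appendix 6, on the Safety Population, for the 2-hour post-dose ECG:
- QTcB and heart rate, with the number of participants contributing to each treatment, since anyone withdrawn after Period 1 has a value for one product only;
- change from screening, with screening stated as the baseline because it is the only scheduled pre-dose ECG;
- counts meeting the protocol's own post-dose criteria in section 8.1.2 (QTcB above 500 msec; change above 60 msec). The 450 msec value in section 6.2 is an eligibility limit and does not belong among the post-dose counts.

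Leave the discharge ECG out of the treatment comparison; it can stay in the listing. A paired test-minus-reference difference in 2-hour QTcB with a confidence interval may be added, but is not needed to close the gap. Haematology needs no new output because its table is already planned.

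If the sponsor intends ECGs only to be listed, the alternative is to say so in section 10.3.5 and narrow the endpoint wording in Table 3 and the synopsis. The recommended route costs one extra table from data already collected, with no new visits or procedures and no change to sample size or alpha.

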### 10.3.6. Other Analyses

No other analyses are planned.

### 10.3.7. Interim Analyses

No interim analysis is planned.

## 12. APPENDICES

### 12.1. Appendix 1: Contraceptive Guidance and Collection of Pregnancy Information

#### Definitions

##### Woman of Childbearing Potential (WOCBP)

A woman is considered fertile following menarche and until becoming post-menopausal unless permanently sterile (see below)

##### Women in the following categories are not considered WOCBP

1. Premenarchal
2. Premenopausal female with ONE of the following:
  - Documented hysterectomy
  - Documented bilateral salpingectomy
  - Documented bilateral oophorectomy
3. Postmenopausal female
  - A postmenopausal state is defined as no menses for 12 months without an alternative medical cause. A high follicle stimulating hormone (FSH) level in the postmenopausal range may be used to confirm a postmenopausal state in women not using hormonal contraception or hormonal replacement therapy (HRT). However, in the absence of 12 months of amenorrhea, a single FSH measurement is insufficient.
  - Females on HRT and whose menopausal status is in doubt will be required to use one of the non-hormonal highly effective contraception methods if they wish to continue their HRT during the study. Otherwise, they must discontinue HRT to allow confirmation of postmenopausal status before study enrolment.

#### Contraception Guidance

##### Male participants

- Male participants with female partners of child-bearing potential are eligible to participate if they agree to ONE of the following during the protocol-defined time frame in Section 6.1:
  - Are abstinent from penile-vaginal intercourse as their usual and preferred lifestyle (abstinent on a long term and persistent basis) and agree to remain abstinent

- Agree to use a male condom plus an additional method of contraception with a failure rate of <1% per year as described in [Table 8](#) when having penile-vaginal intercourse with a woman of childbearing potential
- Men with a pregnant or breastfeeding partner must agree to remain abstinent from penile-vaginal intercourse or use a male condom during each episode of penile penetration for 5 days after each dose of study treatment.
- Refrain from donating sperm for duration of study and for 5 days after the last dose of study treatment

### Female participants

Female participants of childbearing potential are eligible to participate if they agree to use a highly effective method of contraception consistently and correctly as described in [Table 8](#).

**Table 8      Highly Effective Contraceptive Methods**

Highly Effective Contraceptive Methods That Are User Dependent a Failure rate of <1% per year when used consistently and correctly.	
Combined (oestrogen- and progestogen-containing ) hormonal contraception associated with inhibition of ovulation b 
 
• oral
 
• intravaginal
 
• transdermal
 
	
Progestogen-only hormonal contraception associated with inhibition of ovulation b 
 
• injectable
 
	
Highly Effective Methods That Are User Independent	

 
• Implantable progestogen-only hormonal contraception associated with inhibition of ovulationb
 
• Intrauterine device (IUD)
 
• Intrauterine hormone-releasing system (IUS)
 
• bilateral tubal occlusion
 
	
Vasectomized partner (A vasectomized partner is a highly effective contraception method provided that the partner is the sole male sexual partner of the WOCBP and the absence of sperm has been confirmed. If not, an additional highly effective method of contraception should be used.)	
Sexual abstinence (Sexual abstinence is considered a highly effective method only if defined as refraining from heterosexual intercourse during the entire period of risk associated with the study drug. The reliability of sexual abstinence needs to be evaluated in relation to the duration of the study and	

*the preferred and usual lifestyle of the participant.)*

**NOTES:**

- a. Typical use failure rates may differ from those when used consistently and correctly. Use should be consistent with local regulations regarding the use of contraceptive methods for participants in clinical studies.
- b. Hormonal contraception may be susceptible to interaction with the study drug, which may reduce the efficacy of the contraceptive method. In this case two highly effective methods of contraception should be utilized during the treatment period and for at least 30 days after the last dose of study treatment.

**Pregnancy Testing**

- WOCBP should only be included after a confirmed menstrual period and a negative highly sensitive serum pregnancy test
- Additional pregnancy testing should be performed on Day -1 during the treatment period.
- Pregnancy testing will be performed whenever a menstrual cycle is missed or when pregnancy is otherwise suspected
- Pregnancy testing, with a sensitivity of 10 mIU/mL (dipstick) and serum 0.100 to 10 000 mIU/mL (automated) will be performed and assayed in a certified laboratory.

**Collection of Pregnancy Information****Male participants with partners who become pregnant**

- Investigator will attempt to collect pregnancy information on any male participant's female partner of a male study participant who becomes pregnant while participating in this study. This applies only to participants who receive study treatment.
- After obtaining the necessary signed informed consent from the pregnant female partner directly, the investigator will record pregnancy information on the appropriate form and submit it to GSK within 24 hours of learning of the partner's pregnancy.
- Partner will also be followed to determine the outcome of the pregnancy. Information on the status of the mother and child will be forwarded to GSK
- Generally, follow-up will be no longer than 6 to 8 weeks following the estimated delivery date. Any termination of the pregnancy will be reported regardless of foetal status (presence or absence of anomalies) or indication for procedure.

**Female Participants who become pregnant**

- Investigator will collect pregnancy information on any female participant, who becomes pregnant while participating in this study.
- Information will be recorded on the appropriate form and submitted to GSK within 24 hours of learning of a participant's pregnancy.
- Participant will be followed to determine the outcome of the pregnancy. The investigator will collect follow up information on participant and neonate, which will

be forwarded to GSK. Generally, follow-up will not be required for longer than 6 to 8 weeks beyond the estimated delivery date.

- Any termination of pregnancy will be reported, regardless of foetal status (presence or absence of anomalies) or indication for procedure.
- While pregnancy itself is not considered to be an AE or SAE, any pregnancy complication or elective termination of a pregnancy will be reported as an AE or SAE.
- A spontaneous abortion is always considered to be an SAE and will be reported as such.
- Any SAE occurring as a result of a post-study pregnancy which is considered reasonably related to the study treatment by the investigator, will be reported to GSK as described in [Appendix 4](#). While the investigator is not obligated to actively seek this information in former study participants, he or she may learn of an SAE through spontaneous reporting.

Any female participant who becomes pregnant while participating

- will discontinue study treatment or be withdrawn from the study

